9.2. Setting

The study population will include US patients with SCD between the ages of 12 and 85 years who are enrolled in a health insurance plan (commercial, Medicare, Medicaid) continuously during the 365 days prior to and including the index date (baseline) and 180 days post-index. The index selection period is November 25, 2019 (date of Food and Drug Administration [FDA] accelerated approval for voxelotor) through January 31, 2023. The exposed group will include patients with a new prescription claim for voxelotor (no prior use 365 days prior to index date), while the control group will include matched patients who do not have a prescription claim for voxelotor. Non-voxelotor controls will include those receiving no SCD-modifying therapies as well as those receiving non-voxelotor SCD treatments to be reflective of clinical practice. Patients who have a history of stroke will be excluded from this analysis. Both the exposed and control groups may be treated with other SOC treatments such as HU and have 2 or more documented RBC transfusions prior to study index.

Depending on the source of information, approximately 50% of individuals with SCD in the US have received a RBC transfusion, and approximately 20% have received a transfusion in the past year. ¹⁶ In the feasibility assessment of Komodo Healthcare Map (KHM) dataset, race/ethnicity was documented for 90% (n=2230/2486) of patients with 87% (n=1929/2230) identifying as Black or African American. The Centers for Disease Control and Prevention (CDC) estimates 90% of individuals with SCD in the US are non-Hispanic Black or African American. ¹⁷ Socioeconomic status also plays an important factor in impacting patient behavior and access to care. While the KHM dataset does not have direct measures of patients' socioeconomic status, important indicators will be leveraged in the analysis for patients including geography by region, health insurance type, and whether a hematologist is involved in the patient's care. KHM is nationally representative of individuals with SCD. In the Komodo data, approximately 68% of patients have Medicaid as their primary insurance type.

After applying the inclusion/ exclusion criteria, to determine patient index date, the exposed group will index on the first voxelotor prescription claim date and will be sequentially matched using CEM with up to four non-voxelotor patients based on exact age (year) and calendar date to achieve balance between groups. ¹⁸ All exposed patients will be sampled before selecting control patients so that there will be no potential for voxelotor patients to be included in the control group. Age is a critical matching criterion, as individuals with SCD have better access to care before adulthood and accumulate comorbidities through the natural course of the disease. ¹⁹ The matched controls will be selected from the pool of patients who meet all the eligibility criteria below and are the same age (year) on the same day as the

voxelotor claim. Depending on available matches on the same date as the voxelotor claim, an age caliper may be considered to preserve sample size.

Voxelotor individuals will be matched in chronological order where up to four referent non-voxelotor controls will be identified for each voxelotor individuals before additional referent non-voxelotor matches are identified for the remaining exposure group individuals. Individuals will be sampled once to either the matched voxelotor or non-voxelotor cohort and contribute to one group only. This matching approach ensures that all referent individuals are matched to a voxelotor patient on the same date, mitigating potential selection bias by controlling for calendar time and thus any secular trends in available therapies, clinical guidelines, and other confounders that may occur during the study period (e.g., COVID-19 pandemic). Available matches depend on the number of eligible individuals available in the data source.

Index Date1 Exposed: Prescription claim for voxelotor Inclusion Criteria (in prior 365 days): Control: Index date of voxelotor patient match ≥ 2 RBC transfusions Diagnosis of SCD **Exclusion Criteria:** Continuous Enrollment Stroke Pregnant at index Evidence of hemodialysis Continuous Voxelotor Evidence of hematopoietic stem cell transplantation or gene IO. 1801 therapy Inclusion Criteria Renal and/or liver transplant Inclusion/Exclusion Criteria 10.01 1-365, 01 Age ≥ 12 and ≤ 85 years Matching Criteria: Age **Patient Selection Matching Criteria** [0, 0] Covariate Assessment Period³ I-365, 01 **Outcome Assessment Period** [1. censor⁴] Start of study End of study period of interest November 2018 period of interest January 2024

Figure 1. Study Design Schematic

Abbreviations: RBC: Red blood cell; SCD: Sickle cell disease

 Index date for the exposed group will be the date of voxelotor prescription claim date and will be sequentially coarsened-exactmatched with up to 4 non-voxelotor patients based on age and calendar date.

Time

- Continuous voxelotor use defined using the voxelotor ship date and days supply with an allowable gap of at most 45 days (voxelotor arm only)
- 3. The full list of potential covariates including definitions can be found in Table 3.
- 4. Follow-up will end at the earliest of the following events: 365 days after index, death, disenrollment, the occurrence of any exclusion criteria events (e.g., pregnancy, stroke, hemodialysis, evidence of HSCT or gene therapy, renal transplant, or liver transplant), end of data, or discontinuation of voxelotor (voxelotor arm).

This study will use administrative closed claims data between November 2018 (one year prior to voxelotor FDA accelerated approval in the US) and the end of the study period (January 31, 2024; the matched controls will index on the same date of their matched

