9.7.3. Outcome Analysis

Operational definitions for each outcome are described below. Each outcome will be assessed using the primary assessment method for the follow-up period where follow-up will end on the earliest of the following occurrences:

- Disenrollment from health insurance (with a 45-day allowable gap)
- Death
- Discontinuation of voxelotor (with a 45-day allowable treatment gap, voxelotor arm only)
- End of follow-up: up to 1 year from index date (365 days)
- The occurrence of any exclusion criteria events (e.g., pregnancy, stroke, hemodialysis, evidence of HSCT or gene therapy, renal transplant, or liver transplant)

The primary analyses will employ an as-treated follow-up approach that ends follow-up upon treatment changes. Patients will be followed from the index date until treatment change (discontinuation of voxelotor for voxelotor group), or the end of follow-up, whichever is earlier. This as-treated method of analysis allows for an estimate of the effect while the patient is taking the drug of interest and addresses intercurrent events. However, it may introduce bias into the estimates. To adjust for differences in follow-up time between voxelotor patients and their matched controls, matched or pairwise censoring will be applied to censor unexposed on the date of voxelotor discontinuation for their matched pair as a sensitivity analysis.³⁸ A summary of sensitivity analyses is included in Table 7 to evaluate how the magnitude of this bias will be assessed.

Primary Objective - Change in Number of RBC Transfusions PPPY

For each patient, the difference in the number of RBC transfusions PPPY from baseline to follow-up period will be reported as the change and will be calculated as follows:

$$Change = \left(\frac{Number\ of\ RBC\ transfusions\ in\ follow-up}{Available\ days\ of\ follow-up} - \frac{Number\ of\ RBC\ transfusions\ in\ baseline}{365\ days\ *}\right)x\ 365$$

The change in the number of RBC transfusions PPPY will be analyzed using generalized linear model (GLM) with an identity link to estimate the difference in RBC transfusion change rates between the two groups. If any pre-index covariates that are found to be unbalanced after the PS method, it will be included in the regression as a covariate. The rate change and its 95% confidence intervals (CI) will be reported.

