Because this study does not include an active comparator as a control group, CEM will be used to select the index date of matched controls on the initiation of voxelotor for exposed patients. All exposed patients will be selected prior to controls to preserve sample size. Sampling bias may be introduced by prioritizing exposures, but the impact is limited due to a larger pool of untreated control patients than potential exposures. There may be differences in patient characteristics dependent on when patients enter the study population (i.e., initiating voxelotor versus periods without treatment for matched controls). However, PS methods will be utilized to control for observed baseline confounding between the exposed and referent groups. Linked Ouest data will be used to evaluate Hb levels in baseline (an important diagnostic criterion for RBC transfusions). Feasibility analyses will be conducted prior to implementation to assess the number of patients in this study with available Hb data. Assuming a significant number of patients will not have Hb data in baseline, a sensitivity analysis has been proposed to assess the primary outcome among patients with this lab data. However, there may be differences in the frequency of Hb testing between the exposed and control group, relative to when patients enter the study cohort. For most subgroup analyses, the PS obtained from the overall study cohort PS model will be used for PS adjustment. However, for the subgroup of patients with non-missing Hb values in baseline, the PS model will be re-fit and will include an additional covariate (mean Hb value). Depending on the utilization of other SOC treatments in both the exposed and control groups, other subgroup analyses may be conducted. Additionally, the primary analysis will be as-treated, which includes discontinuation of voxelotor as a censoring criterion in the exposed group. This creates potential for confounding via differential censoring between the exposed and referent groups. However, to account for these potential differences in follow-up time, matched censoring will be used to censor matched controls on the date of their voxelotor match's discontinuation date as a sensitivity analysis.

A summary of the potential limitations of the RWD in this study and the mitigation strategies that will be applied is provided in Annex Table 3.

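### Control eligibility depends on whether a patient starts voxelotor after the matched date, which can bias the primary difference by an amount and in a direction the protocol cannot fix

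*Protocol*

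**What the plan says.** Section 9.2 (Setting) gives the exposed arm an explicit 365-day look-back for prior voxelotor use. For the comparator it says only that "the control group will include matched patients who do not have a prescription claim for voxelotor", with no look-back or look-ahead window. On the order of selection, all exposed patients are "sampled before selecting control patients so that there will be no potential for voxelotor patients to be included in the control group". It adds: "Individuals will be sampled once to either the matched voxelotor or non-voxelotor cohort and contribute to one group only". The index period runs from 25 November 2019 to 31 January 2023.

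The follow-up stops in Section 9.7.3 include "Discontinuation of voxelotor (with a 45-day allowable treatment gap, voxelotor arm only"), and the as-treated rule reads "Patients will be followed from the index date until treatment change (discontinuation of voxelotor for voxelotor group"). The note to Figure 1 has the same stop. None of these lists has an event for a control who starts voxelotor.

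Section 9.9 acknowledges part of the issue: "Sampling bias may be introduced by prioritizing exposures, but the impact is limited due to a larger pool of untreated control patients than potential exposures". It gives no figure.

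**The concern.** Whether someone may be a control on a given date should depend only on what is known by that date. Here it depends on the rest of the record. Take two patients who are alike and untreated in January 2020. One starts voxelotor in mid-2020 and is removed from the 2020 control pool. The other never starts and is kept. The control arm is thus selected on its own later course.

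This matters if later starters have a different transfusion course from never-starters. That is plausible from the protocol's own statements. Section 7 says voxelotor raises Hb and that Hb is critical to the transfusion decision. The Table 4 footnotes and Section 9.9 exclude Hb from the primary propensity score model. Baseline propensity adjustment cannot undo selection on events after baseline. None of the Table 7 analyses (ITT, one-year minimum follow-up, matched censoring, subgroups) is described as changing how controls are chosen. The primary estimate is meant to support marketing-authorization decisions, so bias in either direction matters.

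**Working it through.** **Inputs from the protocol**

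- Section 9.5: 185 treated and 370 controls, difference 1.0, SD 3.0, inflation factor 1.65, power 80%.
- Section 9.5: about 7,700 voxelotor-treated among about 94,000 patients with SCD, so 7,700/94,000 = 8.2%. This is the share ever treated among all SCD patients, not the share of eligible controls removed.
- Two-sided alpha of 0.05 is assumed from the 95% confidence intervals.

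**Assumed, because the protocol does not give them**

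- The share of index-eligible untreated patients removed because they start later: 8.2% as a crude anchor and 20% as a higher value.
- The excess *d* of those patients in change in transfusions per patient per year (PPPY): 1 to 3.

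**The plan's own sample size.** Treated n = 1.5 × [3.0 × (1.960 + 0.842)]² / 1.0² = 106, and 106 × 1.65 = 175. The stated 185 is slightly more. With SE = 3.0 × √1.65 × √(1/185 + 1/370) = 0.347, power at 185/370 is 82%. The small gap has no bearing on this point. The SE is used below.

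**Shift in the control mean**

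- If *d* is starters minus never-starters and *f* is the share removed, the shift is *f* × *d*.
- If *d* is starters minus the whole pool and *p* is the share removed, the shift is *p* × *d* / (1 − *p*).

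| Share removed | Formula | d = 1 | d = 2 | d = 3 |
|---|---|---|---|---|
| 8.2% | f × d | 0.08 | 0.16 | 0.25 |
| 8.2% | p × d / (1 − p) | 0.09 | 0.18 | 0.27 |
| 20% | f × d | 0.20 | 0.40 | 0.60 |
| 20% | p × d / (1 − p) | 0.25 | 0.50 | 0.75 |

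**Consequence at the planned size (SE 0.347)**

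| Shift against voxelotor | Power if the true benefit is 1.0 | Two-sided type I error if there is no effect |
|---|---|---|
| 0 | 82% | 5.0% |
| 0.08 | 76% | 5.6% |
| 0.16 | 68% | 7.5% |
| 0.25 | 58% | 11.1% |

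**Simulation check.** One million untreated patients had a change with mean −1 and SD 3.0, partly driven by a latent worsening score (coefficient 1.5 per SD). There was no voxelotor effect. The log-odds of later initiation rose by 0.5 or 1.0 per SD of that score.

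- At 8.2% later starters, removing them moved the control mean by −0.06 and −0.11.
- At 20%, it moved by −0.14 and −0.26.
- At 20% with initiation unrelated to worsening, it moved by about 0.

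The starter-minus-never gaps were 0.73 and 1.38 at 8.2%, and 0.72 and 1.30 at 20%. Share × gap reproduces each shift, for example 0.082 × 1.38 = 0.11.

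**Pool size.** Neither formula contains the size of the pool. It governs how many matches can be found. A larger pool matters here only if it means a smaller share removed, and the protocol gives no such share for eligible patients.

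**The case against.** Several points on the other side carry weight.

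- *The look-ahead window is not written out, and the SAP may define it.* True. But the sampling order, its stated purpose and the one-group-only rule are all fixed in the protocol, and never-user is their plain reading.
- *The protocol does not say who starts voxelotor.* This stands. Section 7 describes the drug's effect on Hb, and Section 9.2 also points to access factors (region, insurance, hematologist involvement). Baseline transfusion count is a listed covariate, which weakens part of the link. The inference is plausible, not documented.
- *The inputs are assumed.* This stands. The relevant *d* is the difference in change over at most 365 days, after matching. Patients who start long after that window may differ little.
- *The limitation is disclosed.* Section 9.9 names sampling bias, but its reason for calling it limited does not address selection on later course.

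Two stronger readings are tempting and are not supported. A reader might infer a second, simultaneous defect: that no control is censored at voxelotor start, so treated time is counted as untreated. If controls are never-users, no control can start, and the missing stop does no harm. It would matter only if the control definition meant claim-free up to index. Some starters could then be sampled as controls, such as those who begin after 31 January 2023 or who fail the 180-day continuous-use criterion. A reader might also infer that the bias is shown to run against voxelotor. It does so only if worsening patients are the ones who start. If later starters do better than average, the sign reverses.

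**Conclusion.** The point holds as a defect of control selection. As written, eligibility for the control arm depends on events after the matched date, and no planned analysis in the protocol removes this. Bias in the primary difference follows if later initiation is related to the transfusion course, which is plausible but not documented.

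The crude 8.2% share with an excess of 1 to 3 PPPY gives the range of about 0.08 to 0.27, or 8% to 27% of the 1.0 target difference. That is modest but enough to matter for power or type I error. A larger removed share would make it larger, and unrelated initiation would make it about zero. The size cannot be stated more firmly from the documents. The claim in Section 9.9 that the larger untreated pool limits the bias should not stand.

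**What to change.** 1. In Section 9.2, define control eligibility only by information up to the matched date: no voxelotor claim on or before it, with the same washout as the exposed arm, whatever happens later.
2. Replace the one-group-only rule. Let a control who later starts voxelotor enter the voxelotor arm at his or her own start date if eligible, and use a patient-clustered robust variance.
3. Because controls can then start voxelotor, add first voxelotor claim (control arm) to the follow-up stops in Section 9.7.3 and Figure 1.
4. Treat that stop as informative, for example with inverse-probability-of-censoring weights, and report the ITT analysis without the stop alongside.
5. Keep very short control follow-up from dominating. The endpoint is a per-patient annualised rate, so one transfusion before a stop on day 10 becomes 365/10 = 36.5 PPPY. Counts with a person-time offset, or person-time weighting, would handle this.
6. Delete the pool-size reassurance in Section 9.9.

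The cost is protocol wording, a re-run of cohort selection on data already held, and a censoring model. Some patients will appear in both arms and some control follow-up will be shorter. Confounding by indication at baseline remains and is not addressed by this change.

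### Giving each voxelotor patient up to four controls in date order, without reuse, can leave later starters unmatched where eligible controls are scarce; assigning in rounds avoids most of this

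*Protocol*

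**What the plan says.** Protocol Section 9.2 (Setting) indexes each exposed patient on the first voxelotor claim and matches "up to four non-voxelotor patients based on exact age (year) and calendar date". Matching runs chronologically, and "up to four referent non-voxelotor controls will be identified for each voxelotor individuals before additional referent non-voxelotor matches are identified for the remaining" exposed patients. Reuse is ruled out: "Individuals will be sampled once to either the matched voxelotor or non-voxelotor cohort and contribute to one group only".

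The section recognises that supply may be short. It notes that "Available matches depend on the number of eligible individuals available in the data source" and that "an age caliper may be considered to preserve sample size", without giving a width or a trigger. Section 9.9 (Strengths and limitations), on selecting exposed patients before controls, says that "the impact is limited due to a larger pool of untreated control patients than potential exposures".

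Three other places bear on the point. Section 9.7.2 targets the ATT and makes variable-ratio 1:2 propensity score matching the primary approach. Section 9.7.1 treats coarsened exact matching as the step that identifies the study populations, before any propensity score work. The amendment table (Section 5, version 2.1) gives the reason for allowing four controls: it lets the propensity score step match up to two.

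**The concern.** The rule depends on order. A control who stays eligible for some time is a candidate for several voxelotor patients of the same birth cohort, and the earliest of them may take up to four such people before the next receives any. The third and fourth are spares for the propensity score step; to the next patient in line, one of them may be the only exact match.

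The protocol does not say outright what happens to a voxelotor patient with no match, but its reference to a matched voxelotor cohort implies that the patient is left out. Such losses would fall more on later index dates and thinly populated ages. The matched set would then no longer represent all eligible treated patients, which is what an ATT describes. Calendar time, which Section 9.2 wants controlled, would instead help decide who is retained. Exposed sample size, which Section 9.9 wants preserved, would fall.

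**Working it through.** **Mechanism.** Take two voxelotor patients of the same birth cohort, one starting later than the other, and four controls eligible on both dates. As written, the first receives four and the second none. In rounds, each receives two. Four controls are used either way, but only rounds keep both patients and give each the two controls that 1:2 matching can use.

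**The plan's sample size, to see the slack.** Section 9.5 gives a difference of 1, SD 3.0, ratio 1:2, power 80% and an inflation factor of 1.65. Two-sided alpha of 0.05 is assumed, since none is stated.

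- n (voxelotor) = (1 + 1/2) × (1.96 + 0.84)² × 3.0² / 1² ≈ 106; 106 × 1.65 = 174.9, so 175 plus 350 controls.
- The stated 185 plus 370 is not reproduced exactly; it errs on the safe side and gives 82.2% power.
- At 1:2, power with 170, 150 and 130 voxelotor patients is 78.9%, 73.7% and 67.6%. At the stated minimum the slack is 185 − 175 = 10 voxelotor patients, about 5%.

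**Pool ratio.** The only counts (Sections 4 and 9.5) are about 94,000 patients with SCD and about 7,700 treated: (94,000 − 7,700) / 7,700 = 11.2 untreated per treated. This precedes the criteria on transfusion history, enrollment, 180-day voxelotor use and exclusions. The eligible ratio, overall or by age and date, is not given.

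**Simulation under assumed inputs.** 200 or 500 voxelotor patients; right-skewed ages from 12; index dates uniform over the 38-month window; each control eligible for one year or for the whole window and ageing with time; exact year of age; no reuse. There were six replicates per setting, so the figures are rough. Ranges run over the four combinations of cohort size and eligibility spell.

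| Eligible controls per voxelotor patient | No control, as written | Earliest third | Latest third | No control, in rounds |
|---|---|---|---|---|
| 2 | 33–40% | 18–35% | 38–48% | 5–25% |
| 4 | 11–19% | 3–14% | 14–23% | 2–8% |
| 6 | 2–11% | 2–7% | 4–12% | 0.4–5% |
| 11.2 | 0.5–2.3% | 0.1–4% | 1–2% | 0.2–1.7% |

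Two further simulations with separately chosen inputs agree in direction at every ratio tried. One, with 400 voxelotor patients, gives 33% against 8% at 2:1, 12% against 2% at 4:1 and 1.4% against 0.8% at 8:1. The other gives 13–19% against 3–8% at 4:1 and 2.6–3.8% against 1.8–3.2% at 11.2:1, with no fewer controls used in total.

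A one-year age caliper applied to everyone (three replicates) lowers the loss at 4:1 to 6–10% as written, with 10–19% in the latest third, against 0.1–2% in rounds.

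Rounds do not win on every measure. At 2:1 with 200 voxelotor patients and one-year eligibility, the share with fewer than two controls was 65% as written and 67% in rounds, because scarce controls were spread over more patients.

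**The case against.** The strongest reply is that the pool is large. At 11.2:1 the loss is small and differs little between early and late starters; the ratios at which it becomes material are assumed. Eligibility could also raise the ratio, since 180 days of continuous use is required of the voxelotor arm only. This stands, and it makes the point conditional. It does not settle the matter: the ratio could equally fall if transfused patients are more likely to start voxelotor. The sentence in Section 9.9 concerns sampling exposed patients before controls, not competition among exposed patients, and no eligible count supports it.

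A second reply is that the protocol has fallbacks. The age caliper helps, but it is optional and relaxes a criterion that Section 9.2 calls critical; changing the order costs nothing in match quality. The weighting fallback in Section 9.7.2 acts on the cohort left after exact matching, so it would not restore patients lost there.

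Some stronger readings are tempting, and the protocol does not support them:

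- A reader might infer that later starters will certainly go unmatched. That cannot be known without the eligible ratio.
- A reader might infer that any later starter of the same age is affected. Because age advances with the date, competition across years is within a birth cohort.
- A reader might infer that third and fourth controls stay tied to one patient. Section 9.7.2 does not confine propensity score matching to the exact-matched sets, and if it is pooled, spares are open to every voxelotor patient still in the cohort. The loss discussed here occurs before that step.
- A reader might infer that the cap of four is an error. It has a stated reason and need not change.
- A reader might infer that the optional caliper contradicts version 1.1. That amendment removed it only as the default.

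**Conclusion.** The concern holds as a conditional risk. The assignment order in Section 9.2 can leave later starters and patients at sparse ages unmatched when eligible controls are scarce, and assigning in rounds left fewer voxelotor patients without a control at every ratio tested. Across the simulations the unmatched share is about 11–19% as written against 2–8% in rounds at 4:1, and about 0.5–4% against 0.2–3% at 11.2:1. These figures rest on assumed cohort sizes, ages and eligibility spells, not on protocol data, and on the implied rule that an unmatched voxelotor patient leaves the analysis.

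The protocol does not show that the study would miss its 185 voxelotor patients: it gives no count of eligible treated patients. If that number were close to 185, a loss of 11–19% would leave about 165 to 150 (185 × 0.89 to 185 × 0.81), with power below 78.9% and down to 73.7% even if 1:2 were kept. The change is worth making because it is nearly free and serves the protocol's own aims.

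**What to change.** In Section 9.2, keep the cap of four and the single use of each person, but assign controls in rounds: one to every voxelotor patient in date order, then a second, a third and a fourth while eligible controls remain. Apply the optional age caliper only to patients still unmatched after round one. State what happens to a voxelotor patient who remains unmatched, and report the number unmatched by index period and age.

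The cost is a small change to the matching loop and a few sentences in Section 9.2. No new data are needed, and the matching keys involve no outcome. The downside is that some early starters receive fewer spare controls for the propensity score step when the pool is scarce.
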